#### **8.4 MULTIPLE COMPARISONS AND MULTIPLICITY**

Experimental wise Type I error rate will be controlled at no greater than 0.05 (for 2-sided hypotheses). The study will include an interim analysis for efficacy when 75% of the pre-specified total adjudicated events have occurred. The primary efficacy endpoint will be tested at an interim analysis with an alpha level of 0.020 (2-sided) and at the final analysis at an alpha of 0.044 (2-sided) with the overall Type I error rate controlled at 0.05. Efficacy boundaries for early stopping of the study are calculated based on the O'Brien-Fleming alpha-spending function.

The effect of treatment will be formally tested on the following 3 key secondary efficacy endpoints:

- Change from Baseline in 6MWD at Week 24
- Change from Baseline in NT-proBNP at Week 24
- Change from Baseline in combined 6MWD/Borg dyspnea score at Week 24

In order to control the Type I error rate, the hierarchical (fixed-sequence) test procedure will be used. The p-value for the change from Baseline in 6MWD at Week 24 will be tested at a 2-sided Type I error rate of 0.05. The subsequent tests for change from Baseline in NT-proBNP at Week 24 and then the change from Baseline in combined 6MWD/Borg dyspnea score at Week 24 will be tested only if the preceding test is statistically significant.

The statistical tests for other secondary endpoints below are considered exploratory and no multiplicity adjustment will be applied. For data collected beyond the specified week (eg, Week 48 for 6MWD, Borg score, WHO FC; Week 24 for RHC hemodynamics; and Week 36 for NT-proBNP), descriptive summaries will be provided with no statistical testing.

- 6MWD at all time points prior to Week 48 (other than Week 24)
- Borg dyspnea score at visits prior to Week 48
- WHO FC at visits prior to Week 48
- RHC hemodynamics at Week 24
- NT-proBNP at all time points prior to Week 36 (other than Week 24)

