10.3.2 Secondary Efficacy Endpoint(s)

The effect of treatment will be formally tested on the following secondary endpoints:

1. Exercise capacity as assessed by 6MWD measured at Week 24
2. NT-proBNP at Week 24
3. Combined 6MWD/Borg dyspnea score at Week 24

In order to control the Type 1 error rate, the secondary efficacy endpoints will be tested using a hierarchical (fixed-sequence) testing procedure. The 6MWD at Week 24 will be tested at a two-sided Type I error rate of 0.05. The subsequent tests for NT-proBNP at Week 24 and then the combined 6MWD/Borg dyspnea score at Week 24 will be tested only if the preceding test is statistically significant. All other secondary endpoints will be summarized using descriptive statistics or analyzed using an exploratory approach.

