##### 10.1.1.1 *Hypothesis*

The study is designed to determine the efficacy of UT-15C compared with placebo in subjects with PAH. The null hypothesis tested for the primary endpoint of time to adjudicated clinical worsening is that there is no difference in hazard ratio in the time to clinical worsening of PAH when treated with UT-15C compared with placebo:

$$H_0: \text{hazard ratio} = 1$$

The 2-sided alternative hypothesis is that there is a difference:

$$H_a: \text{hazard ratio} \neq 1$$

Due to the alpha spending on interim analysis, for the final analysis, the significance level for the primary efficacy analysis of time to adjudicated clinical worsening is 0.044.

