**10.2 KEY SECONDARY EFFICACY MEASURES**

The effect of treatment will be formally tested on the following 3 secondary endpoints:

- Change from Baseline in 6MWD at Week 24
- Change from Baseline in NT-proBNP at Week 24
- Change from Baseline in combined 6MWD/Borg dyspnea score at Week 24

The tests for these 3 key secondary efficacy endpoints will be hierarchical with a fixed sequence approach as described in Section 8.4.

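### SAP 8.4 promises an experiment-wise two-sided error of at most 0.05, but tests Week 24 6MWD at a second 0.05 with no condition on the primary

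*SAP*

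**What the plan says.** SAP 8.4 opens with a general limit: "Experimental wise Type I error rate will be controlled at no greater than 0.05", for two-sided hypotheses. It allocates that limit to time to adjudicated clinical worsening: "The primary efficacy endpoint will be tested at an interim analysis with an alpha level of 0.020 (2-sided"), then 0.044 at the final analysis, for 0.05 overall. SAP 10.1.1.1 repeats that at the final analysis "the significance level for the primary efficacy analysis of time to adjudicated clinical worsening is 0.044".

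SAP 8.4 then names three key secondary endpoints for formal testing: change from Baseline to Week 24 in 6MWD, in NT-proBNP, and in the combined 6MWD/Borg score. On the first it says that the change in "6MWD at Week 24 will be tested at a 2-sided Type I error rate of 0.05". The other two, introduced as the subsequent tests, "will be tested only if the preceding test is statistically significant".

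SAP 10.2 refers back: "The tests for these 3 key secondary efficacy endpoints will be hierarchical with a fixed sequence approach as described in Section 8.4". Protocol 10.3.2 matches it: "the secondary efficacy endpoints will be tested using a hierarchical (fixed-sequence) testing procedure", and "The 6MWD at Week 24 will be tested at a two-sided Type I error rate of 0.05". In both documents the written sequence starts at 6MWD, and the primary is not named as a member of it.

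**The concern.** The primary uses the whole 0.05. A further test at 0.05 stays within an experiment-wise limit of 0.05 only if it is reached through a significant primary, and no such condition is written. A reader following SAP 8.4 literally could miss on the primary, find 6MWD significant at 0.05, go on to NT-proBNP and the combined score, and report all three as formally significant under a procedure said to control error at 0.05.

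What is at stake is the confirmatory status of the three key secondaries. The primary test, its boundaries and its power do not depend on this point.

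**Working it through.** **Inputs from the documents**
- Primary: nominal two-sided levels 0.020 (interim) and 0.044 (final), SAP 8.4. Protocol 10.2 confirms that these are boundaries on the p-value scale. Critical values: |Z₁| > 2.326 and |Z₂| > 2.014.
- Information fraction at the interim: t = 154/205 = 0.751 (SAP 4.2), so corr(Z₁, Z₂) = √(154/205) = 0.867.
- 6MWD: two-sided 0.05, so |W| > 1.960 (SAP 8.4).

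**Assumed**
- The documents give no correlation between the primary and 6MWD statistics. Let ρ = corr(Z₂, W), ranging from 0 to 1, and let corr(Z₁, W) = ρ√t.

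**Step 1: the plan's own figure.** For the primary alone under the null,

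P(|Z₁| > 2.326 or |Z₂| > 2.014) = 0.0501.

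This reproduces the stated overall 0.05; the remaining 0.0001 comes from rounding the boundaries. Nothing is left over for another test.

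**Step 2: the rule as written.** Under the global null, the error is P(primary crosses at either look, or |W| > 1.960). NT-proBNP and the combined score are tested only after 6MWD is significant. They therefore add nothing to this probability, and the result covers all four tests.

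At ρ = 0 this is 1 − (1 − 0.0501)(1 − 0.05) = 1 − 0.9499 × 0.95 = 0.0976.

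Numerical integration over the joint normal distribution gives:

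| ρ (assumed) | P(primary or 6MWD falsely significant) | P(6MWD falsely significant, primary not) |
|---|---|---|
| 0 | 0.0976 | 0.0475 |
| 0.3 | 0.0953 | 0.0452 |
| 0.5 | 0.0910 | 0.0409 |
| 0.7 | 0.0840 | 0.0339 |
| 0.9 | 0.0714 | 0.0213 |
| 1 | 0.0554 | 0.0053 |

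The last column is the union minus the primary's 0.0501. Simulation with 4,000,000 draws agrees (0.0978, 0.0955, 0.0912, 0.0841 and 0.0716 for ρ from 0 to 0.9). The excess survives at ρ = 1 because 6MWD is tested at 0.05 while the final primary is tested at 0.044.

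**Step 3: sensitivity to the interim correlation.** At ρ = 0.9 the union is about 0.069 if both looks correlate 0.9 with 6MWD, and about 0.076 if the 0.9 applies to the interim look instead. All of these exceed 0.05.

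**Step 4: with a gate on the primary.** Under the global null, any false rejection among the four tests then requires a false rejection of the primary, so the error is 0.0501 at every ρ. The case of an effective primary and a null 6MWD was simulated with primary drift 0 to 6, ρ from 0 to 0.9, and an assumed 0.75, 0.9 or 1.0 of the 6MWD information available if the trial stops at the interim. The largest two-sided 6MWD error was 0.0501, which is 0.05 within simulation error.

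**The case against.** The strongest reply is that the gate is implied. SAP 8.4 opens with an experiment-wise limit, takes the primary first, and says the hierarchy serves to control Type I error; read as a whole, the sequence would begin at the primary. It is true that the documents omit the gate and do not rule it out. But the condition is written for NT-proBNP and the combined score, 6MWD has its own free-standing 0.05, and SAP 10.2 and Protocol 10.3.2 place only the secondaries in the sequence. The implied reading has to be supplied by the reader.

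Three narrower points stand:
- The protocol makes no experiment-wise promise, so the contradiction lies in the SAP; changing the protocol is for alignment.
- Correlation 0 is the least plausible end of the range, because the primary composite contains 6MWD criteria. A positive correlation reduces the excess without removing it.
- The rates above are two-sided. Counting only false results that favour UT-15C, the union is about 0.049 at ρ = 0 and 0.036 at ρ = 0.9, against about 0.025 for the primary alone.

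The gate also has a limit. With an effective primary, a null 6MWD, ρ = 0.9 and 75% of the 6MWD information at an interim stop, false favourable 6MWD findings can reach about 0.030 in that one tail (about 0.027 at 90% information and 0.025 at 100%). SAP 8.4 makes only a two-sided promise, which the gate meets, so this does not undo the fix.

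**Conclusion.** The concern holds. SAP 8.4 states a property that its written testing rule does not deliver. Under the global null the experiment-wise two-sided error is 0.098 to 0.071 for assumed correlations of 0 to 0.9, and 0.055 at correlation 1, against the promised 0.05. The exact size rests on the assumed correlation, including how the interim statistic relates to 6MWD; the direction does not, since every value tried exceeds 0.05. The chance of a false 6MWD claim beside a failed primary is 0.0475 to 0.0213 over correlations 0 to 0.9. The flaw should be fixed, but it is confined to the standing of the three key secondaries.

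**What to change.** Make the primary the first step of the sequence in SAP 8.4, and have SAP 10.2 follow it. Suggested text: *Key secondary endpoints are formally tested, in the stated order, only if the primary endpoint is significant at its interim or final boundary, and once only, in the analysis after database lock (Section 4.3); otherwise all secondary p-values are nominal.*

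The cost is one SAP sentence, to be added before database lock and sponsor unblinding. Protocol 10.3 leaves further analysis detail to the SAP, so Protocol 10.3.2 can be aligned at the next amendment, which under Protocol 13.1 needs regulatory and IRB/EC approval. The downside is that no formal secondary claim is possible if the primary fails, which the limit in SAP 8.4 already entails.

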## 8.5 DERIVED AND TRANSFORMED DATA

Time to Clinical Worsening will be derived as follows:

Parameter	Scenario	Formula	Status
Time to Clinical Worsening (weeks)	Subjects with clinical worsening event reported during the study that is adjudicated/confirmed	= (Worsening date – Randomization date)/7 Note: for subjects with clinical worsening due to worsening 6MWD, the clinical worsening date is date of the second/confirmatory 6MWT	0 (event)
	Subjects who died during the study	= (Death date – Randomization date)/7	0 (event)
	Subjects with clinical worsening event reported during the study that is adjudicated as not meeting the clinical worsening event criteria by the adjudication committee	For analysis of investigator reported clinical worsening event: = (Worsening date – Randomization date)/7	0 (event)
		For analysis of adjudicated clinical worsening event: = (Last assessment date – Randomization date)/7	1 (censored)
	Subjects without clinical worsening event during the study	= (Last assessment date – Randomization date)/7	1 (censored)
Subjects discontinued from the study prematurely that did not have a clinical worsening event	= (Last assessment date – Randomization date)/7	1 (censored)	

For subjects with clinical worsening due to the decrease from Baseline in 6MWD, confirmatory 6MWT should be conducted. The event time is based on the date of the

confirmatory 6MWT. As a sensitivity analysis, the event time based on the date of the first reported 6MWT will also be performed.

Hemodynamic parameters will be derived as follows:

Parameter	Formula
Cardiac index in L/min/m 	= cardiac output (CO) Fick / body surface area (BSA)
Systemic vascular resistance (SVR) in dynes*sec/cm 	=80 * (systemic arterial pressure mean [SAPm] – right atrial pressure mean [RAPm]) / CO Fick
SVR index (SVRI) in dynes*sec/cm  /m 	=80 * (SAPm – RAPm) / cardiac index
Pulmonary vascular resistance (PVR) in dynes*sec/cm 	=80 * (Pulmonary artery pressure mean [PAPm] – Pulmonary capillary wedge pressure mean [PCWPm]) / CO Fick
PVR Index (PVRI) in dynes*sec/cm  /m 	=80 * (PAPm – PCWPm) / cardiac index

Electrocardiogram parameters will be derived as follows:

Parameter	Formula
QTc (Bazett)	$= QT / \sqrt{\frac{60}{HR}}$
QTc (Fridericia)	$= QT / \sqrt[3]{\frac{60}{HR}}$

## 8.6 ASSESSMENT WINDOWS

### 8.6.1 Assessment Windows for Scheduled Visits

The study protocol included visit windows of +/- 7 or 14 days. However, for any data summarized by scheduled visit, an analysis visit window (proposed in the table below) will be used. The scheduled visits, as recorded on the eCRFs, and the corresponding target days and study day intervals are specified in Table 8-1. The analysis visit window will be derived based on the information specified in Table 8-1.

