1.2.4 Efficacy and Safety Data

UT-15C has previously been evaluated in three randomized, placebo-controlled Phase 3 studies (TDE-PH-301, TDE-PH-302, and TDE-PH-308). Additionally, subjects completing these studies have been provided long-term access to UT-15C in an open-label extension study (TDE-PH-304). To date, over 1000 PAH patients have been exposed to study drug (UT-15C or placebo) in the TDE-PH-301, TDE-PH-302, and TDE-PH-308 studies and over 890 patients have received UT-15C in the open-label extension study.

TDE-PH-301 was a 16-week, randomized, double-blind, placebo-controlled, international Phase 3 efficacy and safety study of treprostinil diethanolamine (UT-15C), in patients with PAH. Patients received UT-15C or placebo BID in combination with an ERA, a PDE5-I, or both. The primary endpoint was placebo-corrected change in 6MWD from Baseline to Week 16. Secondary endpoints included Borg dyspnea score, dyspnea-fatigue index, WHO Functional Class, and time to clinical worsening. Study drug dose was titrated up to a maximum of 16 mg BID based on clinical response and study drug tolerability.

Three-hundred fifty-four subjects were enrolled with 30% receiving an ERA alone, 25% a PDE5-I alone, and 45% both agents. The population was 81% female, predominantly WHO Functional Class III (76%), and had a mean baseline 6MWD of 346 m. PAH etiology included idiopathic or heritable PAH (66%), or PAH associated with CTD (26%), repaired congenital systemic-to-pulmonary shunt (7%), or HIV infection (1%). There were no remarkable demographic differences between treatment groups.

Twenty-two percent of subjects discontinued UT-15C therapy compared to 14% in the placebo group. The primary reason for discontinuation was AEs: 14% in the UT-15C group compared to 5% in placebo. There were three deaths in each of the treatment groups.

The Hodges-Lehmann (H-L) estimate of 6MWD placebo corrected median change from baseline at Week 16 was +11 m ($p=0.072$). The change in 6MWD was significant at Week 12 (+13 m, $p=0.015$). The lack of significance at Week 16 may be attributable to the number of subjects who did not provide an efficacy measure at Week 16 due to discontinuing from the study prematurely.

Secondary endpoints of the combined 6MWD and Borg dyspnea score and the dyspnea-fatigue index demonstrated statistically significant changes at Week 16 for UT-15C compared to Baseline ($p=0.013$ and 0.01 , respectively).

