- ^l The Study Termination Visit includes the study drug termination which should be pconducted at the time the decision is made to discontinue the study drug (prior to down titration), either because the subject has met clinical worsening criteria or is being permanently discontinued from the 310 study. The 6MWD should be conducted within 3 to 6 hours after the most recent dose of study medication and preferably before the drug is down titrated (if the subject is being permanently discontinued rather than transitioning to the TDE-PH-311 study)
- ^m If subject permanently discontinues study drug before Week 24 and is ineligible for the TDE-PH-311 study, subject should be encouraged to remain in study and attend visits up to and including Week 24. The end of study assessments (survival status, AE assessment, drug accountability, concomitant medications, etc.) should be conducted after the subject has stopped taking the study medication (before or at Week 24)
- ⁿ Weekly telephone contact should be completed and subject study drug dose must also be recorded at Week 16 and Week 20 in the eCRF. More frequent telephone calls may be necessary depending on the frequency of dose titration and to manage AEs or signs and symptoms of disease
- ^o For subjects consenting to the optional biomarker samples.
- ^p For subjects consenting to the optional pharmacogenomic sample.

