**Table 8-1 Assessment Windows for Scheduled Visits**

Visit	Target Study Day	Study Day Interval
ECGs and hemodynamics:		
Baseline	1	Study Day $\leq 1$ (prior to the first dose)
Week 24	169	$148 \leq$ Study Day $\leq 190$
Clinical laboratory assessments and NT-proBNP:		
Baseline	1	Study Day $\leq 1$ (prior to the first dose)
Week 12	85	$2 <$ Study Day $\leq 127$
Week 24	169	$127 <$ Study Day $\leq 211$
Week 36	253	$211 <$ Study Day $\leq 337$
Week 60	421	$337 <$ Study Day $\leq 505$
Weeks 84, 108, etc	589, 757, etc	(Target Study Day $\pm 84$ days)
6MWT, WHO FC, and vital signs:		
Baseline	1	Study Day $\leq 1$ (prior to the first dose)
Week 4	29	$15 \leq$ Study Day $\leq 43$
Week 8	57	$43 <$ Study Day $\leq 71$
Week 12	85	$71 <$ Study Day $\leq 127$
Week 24	169	$127 <$ Study Day $\leq 211$
Week 36	253	$211 <$ Study Day $\leq 295$
Weeks 48, 60, etc	337, 421, etc	(Target Study Day $\pm 42$ days)

Note: Study Day = (Assessment Date) - (First Dosing Date) + 1

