### 12.1 EXTENT OF EXPOSURE

All study drug dosing will be listed for all subjects. The listing will include initial dose and date of this initial dose, dose and date of each change, and whether each change applied to the morning, afternoon, or evening doses. Dosing at Weeks 4, 8, 12, 24, and every 12-week follow-up assessment will be summarized for subjects still receiving study drug at each of these assessments. A summary by treatment group of maximum study drug dose and overall duration of exposure will be included. The study drug dosing and exposure by the use of background PAH therapy will be provided in a separate summary.

In addition, a summary table will be provided for study drug treatment compliance for the first 24 weeks by treatment group. The summary will include the number and percent of days subjects are dosed and total study drug consumed for first 24 weeks.

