## **12.6 ELECTROCARDIOGRAMS**

All ECG assessments will be listed for all subjects. This listing will include the heart rate, QT interval, QTc interval (calculated using formulas by both Bazett and Fridericia as described in Section 8.5), PR interval, QRS duration, whether there were clinically significant changes from Screening visit, whether abnormalities were present, and details and comments on any abnormalities. The ECG results at each assessment and changes at Week 24 will be descriptively summarized by treatment group. In addition, for QTc interval calculated using both the Bazett and Fridericia methods, the number and percent of subjects with values  $\geq 500$  msec and the number and percent of subjects with changes of  $< 30$  msec, 30 to  $< 60$  msec, and  $\geq 60$  msec will be presented by treatment group.

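### The by-visit laboratory, vital-sign and ECG summaries pool values taken before and after drug was stopped, and the window rules can discard the on-drug value

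*SAP*

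**What the plan says.** SAP 8.6.1 sets the scope of the windows: "for any data summarized by scheduled visit, an analysis visit window (proposed in the table below) will be used". Laboratory, vital-sign and ECG summaries are therefore included. Table 8-1 defines the clock from first dose alone: "Note: Study Day = (Assessment Date) - (First Dosing Date) + 1". Where several values fall in one window, 8.6.2 takes the one nearest the target day, and the later one if two are equally near.

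The safety sections add no limit. SAP 12.5.1 and 12.5.2 summarise laboratory values, changes and shifts at each assessment by treatment group, and 12.7 does the same for vital-sign values and changes. For ECGs, 12.6 says: "The ECG results at each assessment and changes at Week 24 will be descriptively summarized by treatment group". The Safety Population in SAP 6 groups subjects by treatment received and sets no end to the exposure period.

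Visits after stopping are planned. For a subject who stops drug before Week 24 and cannot enter the extension, Protocol Table 3-1, note m, says the "subject should be encouraged to remain in study and attend visits up to and including Week 24". Protocol 7.4 repeats this for stops for any reason other than clinical worsening. It places the termination assessments (laboratory tests, ECG and vital signs among them) before down-titration.

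**The concern.** A by-visit safety table is usually read as showing what happens to subjects taking the drug. Here the UT-15C column at a given visit mixes subjects on drug with subjects who stopped earlier and returned for the visit. If a laboratory, blood pressure, heart rate or QTc effect reverses after stopping, the mean change is pulled toward zero and fewer shifts are counted. Stopping for AEs was more frequent on UT-15C in TDE-PH-301, so the mixing may be unequal between groups.

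The rule also does more than add off-drug values. Because it prefers the value nearest target, it can drop the on-drug measurement taken at the termination visit in favour of one taken weeks later off drug.

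The SAP draws the on-drug distinction elsewhere. Dosing "will be summarized for subjects still receiving study drug at each of these assessments" (12.1), carried-forward values must be on treatment (8.6.2), and the rank analysis of walk distance drops values after termination (10.2.1). That last rule refers to Section 8 for its description, and Section 8 contains no such text.

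**Working it through.** **Windows reproduced.** Target day = 7 × week + 1, so Week 12 = 85 and Week 24 = 169. The limits are midpoints between targets: (85 + 169)/2 = 127 and (169 + 253)/2 = 211. The ECG window is 169 ± 21 = 148 to 190. All agree with Table 8-1, and none contains a last-dose term. There is no Week 12 ECG window, because no ECG is scheduled then.

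**The 8.6.2 rule applied to hypothetical subjects.** Assume the termination visit and the stop fall on the same day; a taper would shorten the off-drug times below.

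- Stop on Day 40, visits attended on Days 57, 85 and 169.
  - Laboratory: Day 40 lies in the Week 12 window (Days 3 to 127) but is 45 days from target. The Day 85 value, taken 45 days after stopping, is used. At Week 24 the Day 169 value is used, 129 days after stopping.
  - Vital signs: the Week 8, 12 and 24 values are all off drug.
  - ECG: Day 40 is in no post-Baseline window, and SAP 8 leaves such values out of summaries. The Day 169 off-drug ECG supplies the Week 24 change.
- Stop on Day 20, visit on Day 29. Both days lie in the vital-sign Week 4 window (Days 15 to 43). Day 20 is 9 days from target and Day 29 is on target, so the off-drug value is used.
- Stop on Day 150, visit on Day 169. The on-drug ECG lies in the window but is 19 days from target. The off-drug ECG is used.

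**Share of Week 24 values that are off drug.** Let d be the fraction stopped and r the fraction of stoppers who attend, with everyone else attending on drug. Then share = d·r / (1 − d + d·r). The d values are the AE stops in TDE-PH-301 (Protocol 1.2.4): 14% UT-15C and 5% placebo. The documents give no r, so the full range is shown.

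| r | UT-15C, d = 0.14 | Placebo, d = 0.05 |
|---|---|---|
| 0 | 0% | 0% |
| 0.25 | 3.9% | 1.3% |
| 0.50 | 0.07/0.93 = 7.5% | 0.025/0.975 = 2.6% |
| 0.75 | 10.9% | 3.8% |
| 1.00 | 14.0% | 5.0% |

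**Effect on a summary.** Suppose the drug effect is fully lost off drug and stopping placebo changes nothing. The observed difference is then (1 − share) × the on-drug difference, using the UT-15C share, so the factor runs from 1.00 to 0.86. An assumed 5-point excess in abnormal shifts would appear as at least 5 × 0.86 = 4.3 points.

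**The case against.** Summarising everyone by treatment received is a recognised choice, and these tables are descriptive: no test, alpha or stopping rule depends on them. The dose summary is limited to subjects on drug because there is no dose to report afterwards, and the carry-forward and walk-distance limits concern efficacy. None of this proves that a safety rule was wrongly left out. That stands. But the SAP does not declare the choice for safety measurements, and the case for a change does not need these contrasts. It rests on the rule preferring an off-drug value to an available on-drug one.

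A reader might infer more than the documents support:

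- That the tables present off-drug values as on-drug. No table carries that label; the values are pooled without distinction.
- That any safety signal is diluted. AE, serious AE and death tables are not windowed. The listings keep every laboratory, ECG and vital-sign value.
- That ECGs are affected at Week 12. Only Week 24 is.
- That the QTc categories are certainly affected. SAP 12.6 counts subjects without naming a visit, so a termination ECG might count. They are affected only if taken from the Week 24 window.
- That 12–22% of UT-15C Week 24 values are off drug. This comes from all-cause stopping: "Twenty-two percent of subjects discontinued UT-15C therapy compared to 14% in the placebo group". With 50–100% attendance it gives 0.11/0.89 = 12.4% to 22%. However, subjects who die, clinically worsen or withdraw consent would not supply these visits, and attendance is only encouraged.

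Even the 14% may be too high. TDE-PH-301 started at 1 mg with 1 mg steps. The protocol reports 0% AE discontinuation (n=23) among subjects with 0.25 mg tablets at randomization, and this trial uses smaller steps. In the other direction, TDE-PH-301 lasted 16 weeks, not 24.

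**Conclusion.** The point holds for by-visit safety summaries: vital signs from Week 4, laboratory values and shift tables at Weeks 12 and 24, ECG change at Week 24, and QTc categories if drawn from that window. These pool off-drug with on-drug values, and on-drug termination values can be displaced or lost from the summaries. The problem is mainly confined to data up to the Week 24 window, since planned attendance after stopping ends there.

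The size cannot be known from the documents. The illustration of 0–14% on UT-15C and 0–5% on placebo rests on AE stops in an earlier trial and on unknown attendance. The matching understatement further assumes that the effect reverses fully off drug and that stoppers would otherwise have shown the average effect. A persistent or delayed effect would not be diluted; a larger effect in those who stopped would be understated by more.

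This is an inexpensive improvement to make before unblinding. It does not threaten the trial's conclusions.

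**What to change.** - In SAP 8.6.1, flag each laboratory, vital-sign and ECG value as on treatment (up to last dose plus a stated number of days) or after treatment. Apply the flag before the nearest-to-target rule in 8.6.2.
- Summarise on-treatment values by visit, with after-treatment values in a separate row.
- Add a row for the last on-treatment value, so that termination-visit values of early stoppers are kept, including ECGs outside Table 8-1. State in 12.6 which ECGs feed the QTc categories.
- Insert in Section 8 the exclusion text that 10.2.1 cites.
- Reconcile Protocol 4.3.1. It says that a subject given a second oral PAH therapy before Week 24 stops study drug and is encouraged to stay for visits. It also says that a subject given one at any time during the study must be discontinued from the study. Which applies decides whether these off-drug values exist.

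The cost is SAP wording, one derived flag and some added rows; SAP 9.1 already lists the last-dose date. The downside is that the on-treatment visit rows hold fewer and more selected subjects, mainly those who tolerated the drug. A cut at last dose alone would hide that selection; the last on-treatment and after-treatment rows make it visible.
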